### **Healthy subjects screening:**

Given that the healthy group of males should match patients with ASD on age, sex and intellectual quotient (IQ), we will first contact patients (from the data base of the previous protocol 64623) and see who is interested and eligible before selecting the matching healthy men controls. We will select healthy participants who already participated in our previous research study (64623). We will use the information collected in project #64623 to match their IQ and age. We will contact participants who agreed to be contacted in the future studies in the consent form of protocol 64623. We will contact healthy subjects by phone and/or email (again from the data base of 64623) to see if they would be interested to participate and whether they are eligible (based on eligibility criteria for healthy subjects and based on safety screening). We will follow a phone script and email for recruitment for healthy subjects. We will respond to email requests for info and include screening form attached.

Given that mid-way study, we have trouble bringing back healthy participants who have participated previously in protocol 64623, we need to recruit new people from general population in Atlanta. We will use flyers to recruit more people. We will post these flyers in different locations around Atlanta area (like in restaurants, college, Marta stations etc). We will need to conduct the IQ test and color blindness prior their main visit to the hospital. Healthy controls should match ASD patients with IQ and race. We are adding race so that samples from both groups stay matched as much as possible.

We have already conducted the total number of patients for this study. The average IQ of ASD patients is 98.39 and the standard deviation is 16.28. The race ratio for ASD is 82% white, 12.5% African American and 6% more than one race,

Accordingly, we are adding a new informed consent and another inclusion criterion for this separate group of healthy subjects (labeled II). The inclusion criteria will include Caucasian race and IQ range between 70 and 115.

The reason that we are adding Caucasian to the inclusion criteria for this new set of healthy subjects is that we have already 2 or 3 contacts from the previous study who are African American and who are interested to participate. This will make approximately 10% of the healthy subject's sample if we were able to recruit 30 total.

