### **Randomization and blinding**

**Clinical trial for ASD subjects:** The trial will be a double-blind, placebo-controlled, several doses of oxytocin, within subject design study. Patients will undergo 4 clinical visits (in addition to a first pre-clinical visit) during which they receive 12 puffs (6 in each nostril) of 8IU total, 24IU and 48IU oxytocin (syntocinon) and placebo (assigned randomly). The placebo will contain the same ingredients as syntocinon, except the active molecule oxytocin. This is essential for making sure that the patient does not recognize the type of treatment he is receiving. Hence, both patients and the experimenter will be blind to the type of the treatment administered.

The pharmacy IDS of Emory will be in charge of the randomization sequence and one of the staff members of the team (who is not involved in testing procedures) will be de-blinded.

We will break the blind after testing 25 patients with ASD to check the results half-way for a mid-point analysis. The mid-point analysis will focus on measures where effect sizes are anticipated to be large enough that the risk of false positives is minimal. We are expecting larger effect size on some measures and therefore we break the blind for those measures to be analyzed and published. Additional data on these measures will continue to be collected and we will attempt to publish the combined analysis at the end to avoid publication bias.

However, the data collection will continue until a sample size equal to 50. Given that we are facing challenges with ASD recruitment and that the study requires the participation in 5 long visits, it is possible that the study will stop at N=30 or 40, in case the PI was not able to recruit more ASD. We also expect dropouts after recruitment. We believe that we will be able to test 30 patients with ASD.

It is possible that this project will be funded by other grant funds which will allow adding more participants (more 50 ASD). In this case, the PI will submit an amendment accordingly.

**Healthy subjects:** There will be only one clinical visit for healthy subjects and they will all receive placebo spray (12 puffs, 6 per nostril). The study will be conducted in a single-blind design. The PI is aware that the subject is receiving placebo. However, the participant will be told that he might

receive oxytocin or placebo. This is important in order to control for the placebo effect on behavior and brain activity.

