### **Statistical analysis:**

Power analysis (using G power 3.1 software) shows that a sample size of 50 subjects with ASD receiving 4 different treatments is needed to reliably detect (95% power) effect sizes small or larger (Cohen's  $d=0.2$ ) on one measure. In this study, we expect to find small to medium size effects of oxytocin inhalation on behavioral measures (based on previous meta-analysis of Bakermans-Kranenburg and Van I Jzendoorn. 2013). Authors found a combined effect size of  $d=0.32$  (95% confidence interval: 0.18-0.47). As mentioned above, we are planning to break the blind with  $N=25$  ASD subjects for a mid-way analysis, which is sufficient to detect effect sizes between medium and small (Cohen's  $d=0.3$ ). We expect larger effect sizes on measures of brain

activity (BOLD activity and functional connectivity). Therefore, these measures will be mainly analyzed during the mid-way analysis for potential publications. Of note, we are also planning to publish the combined analysis with the total number of subjects on the measures that were published mid-way to avoid any publication bias.

For healthy subjects, we need at least 30 subjects receiving on treatment to reliably detect (95% power) the differences between social and non-social conditions or emotional faces versus neutral faces in the aims above with an effect size between small and medium (Cohen's  $d=0.35$ ).

When comparing healthy subjects to patients with autism (placebo administration only), the above numbers are sufficient to reliably detect small effect sizes between groups (Cohen's  $d=0.2$ ) for one measure.

The PI will submit an annual report to the IRB and address whether the study is safe and whether it is appropriate to continue. This report will include compliance, review of eligibility, treatment review, summary of responses, survival, adverse events and safety monitoring rules.

Given that we do not expect serious adverse events and we are investigating the effects of this hormone on brain activity and behavior, we do not expect an early stopping.

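### The combined analysis reduces but does not remove publication bias: the promise in the Statistical analysis section covers only measures published mid-way, and the analysis includes the 25 mid-way patients

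*Combined protocol and SAP*

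**What the plan says.** Randomization and blinding sets the mid-way look: "We will break the blind after testing 25 patients with ASD to check the results half-way for a mid-point analysis". The measures are to be those with large anticipated effects. The Statistical analysis section identifies them as BOLD activity and functional connectivity, and says "these measures will be mainly analyzed during the mid-way analysis for potential publications".

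The two sections describe the later combined report differently:

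- **Statistical analysis:** the intention is to "publish the combined analysis with the total number of subjects on the measures that were published mid-way to avoid any publication bias". The scope is what was published.
- **Randomization and blinding:** "we will attempt to publish the combined analysis at the end to avoid publication bias". The scope here is the measures for which the blind was broken, which is wider, but the commitment is only to try.

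A later paragraph of the Statistical analysis section says that the primary outcomes of the aims are analysed mid-way and that analysis is repeated at the final stage. It does not say what will be published from that final stage.

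On sample size, Randomization and blinding says "However, the data collection will continue until a sample size equal to 50", then that "it is possible that the study will stop at N=30 or 40", then "We believe that we will be able to test 30 patients with ASD". Healthy subjects screening reports "We have already conducted the total number of patients for this study" but gives no final number. No analysis restricted to patients enrolled after the look is described.

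**The concern.** Publication bias arises when what is reported depends on what was found. A rule that re-reports only measures already in print leaves that dependence in place, in two ways.

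1. A measure unblinded at 25 and left unpublished, perhaps because it showed nothing, has no promised combined report under the Statistical analysis wording.
2. A measure that was published is re-estimated in a data set that contains the patients who produced the published result. If a favourable result prompted publication, part of that favourable chance stays in the combined estimate.

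The brain measures are the primary outcomes of aims 1 to 3. A reader told that the combined paper avoids publication bias may take it as a fresh test of the mid-way paper, when half or more of its patients are the same people.

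**Working it through.** The plan gives no figure for this carry-over, so there is none to reproduce.

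**Inputs from the documents.** Mid-way n = 25. Final N = 50 (planned), 40 or 30 (named as possible; 30 is the number the investigators believe they can test). The final N is not stated, so all three are shown.

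**Assumptions.** Two-sided alpha 0.05 (none is stated). One measure, one paired comparison, normal differences. Strict publication rule: a measure is published mid-way only if p<0.05 at n = 25. No passage states such a rule; it is used to show how large the effect could be.

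**Step 1: share of mid-way patients.** The combined mean is (25 × mid-way mean + (N − 25) × later mean) / N, so the mid-way estimate has weight 25/N.

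| N | 25/N | later patients |
|---|---|---|
| 50 | 50% | 25 |
| 40 | 62.5% | 15 |
| 30 | 83% | 5 |

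**Step 2: no true effect, strict rule.** Chance that a significant mid-way result is again significant, in the same direction, in the combined data:

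| N | paired t, simulated | bivariate normal, correlation √(25/N) | later patients alone |
|---|---|---|---|
| 50 | 32% | 34% | 2.5% |
| 40 | 41% | 43% | 2.5% |
| 30 | 61% | 62% | 2.5% |

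The two methods agree to within about two percentage points. The complement is the share of chance findings that would no longer be significant in the same direction: 68%, 59% and 39%.

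**Step 3: true standardised paired effect 0.3, strict rule.** In simulation, a positive result significant at n = 25 has a mean estimate of 0.52, and later patients average 0.30. Put into the formula of step 1:

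- N = 50: (25 × 0.52 + 25 × 0.30)/50 = 0.41
- N = 40: (25 × 0.52 + 15 × 0.30)/40 = 0.44
- N = 30: (25 × 0.52 + 5 × 0.30)/30 = 0.48

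The excess over 0.30 is 0.22 mid-way and 0.11, 0.14 or 0.18 in the combined data. The combined analysis therefore removes about half of the excess at 50 patients and about one sixth at 30.

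**Step 4: publication independent of the result.** The patients behind a published measure are then not a selected set. The combined estimate is unbiased, and the final test taken alone keeps its 5% error rate per measure; the simulation without conditioning gives 5.0% at each N.

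**Step 5: precision of the later patients alone.** The 95% half-width in SD units is t(0.975, n − 1)/√n. With 5 patients it is 2.776/√5 = 1.24; with 15 it is 0.55; with 25 it is 0.41.

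**The case against.** Much of the case on the other side stands.

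- **A cumulative final analysis is normal practice.** Reusing interim patients does not by itself distort the final test (step 4). A reader might infer that the combined test has an inflated error rate; run and reported whatever the mid-way result, it does not.
- **The combined report helps.** Without it, the 0.52 of step 3 would stand uncorrected. A reader might infer that the combined analysis does nothing against the bias, or that a chance result mostly survives. At the planned 50 patients neither is true: about half of the excess goes, and about two thirds of chance findings lose significance.
- **Selection on significance is not in the plan.** Mid-way measures are chosen in advance by type and expected size. A reader might infer that favourable results led to publication, but no passage says so. It is not excluded either, because publication is described only as potential and no rule requires it whatever the result.
- **The final analysis is not confined to published measures.** The Statistical analysis section repeats the analysis at the final stage, and Randomization and blinding uses the wider scope. This narrows the gap to what is promised for publication, but does not close it: the explicit sentence is limited to published measures, and the wider one is only an attempt.
- **The simulation is simpler than the planned imaging analysis.** Aim 1 uses a treatment-by-network ANOVA followed by contrasts, with multiple-comparison correction. The percentages apply to a single contrast. The weights 25/N do not depend on the test.

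**Conclusion.** The point holds in limited form. The combined analysis reduces publication bias, but the plan claims that it avoids it altogether, and the rule as written cannot do that. Two gaps rest on the text alone: unblinded but unpublished measures have no firm promise of a combined report, and the mid-way patients supply 50%, 62.5% or 83% of the combined sample at 50, 40 or 30.

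The size of any bias depends on something the plan leaves open. It is nil if publication did not depend on the result. Under the strict rule, with alpha 0.05 and a single paired test assumed, it reaches the figures in steps 2 and 3; partial dependence falls between. The documents do not support saying that selective publication took place, or that the combined result would mostly repeat a chance finding at the planned size.

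How alpha should be divided between the two looks is a separate question. Settling it would not by itself decide which measures are reported.

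**What to change.** 1. In both Randomization and blinding and Statistical analysis, use the same commitment: the final all-patient analysis will be reported for every measure unblinded at 25 patients, whether or not it was published mid-way. List those measures.
2. Replace the publication-bias rationale in both places with a statement that the combined estimate includes the mid-way patients and is not independent confirmation of the mid-way result.
3. For each of those measures, show the estimate and 95% CI for patients 26 onward as a descriptive supplement, with a note on precision. If the final number is near 30, it rests on about five patients with a half-width of about 1.2 SD, and should not be presented as a test of the mid-way finding.

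The cost is wording in two sections and one extra row per results table. No patients, visits or procedures are added, and the plan already foresees amendments on analysis detail. The price is a less favourable presentation: null measures will appear, and readers will see how little of the evidence is new.

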**Aim 4: Plasma oxytocin concentration and exposome/metabolome**

Here we hypothesize that IN-OT will enhance plasma oxytocin concentration in a dose dependent fashion.

Primary outcome measure: We will investigate the differences between treatment conditions in oxytocin plasma concentration. We expect to find that higher doses of IN-OT will enhance significantly the plasma OXT concentration as compared to lower dose of IN-OT and to placebo.

Secondary outcome measure: We will study the differences between healthy subjects and patients with ASD in terms of baseline oxytocin concentration. We expect significant difference and reduced levels of OXT at baseline in ASD.

different nature of social dysfunctions.

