## **Participant selection:**

50 ASD between the ages of 18 and 45 will participate in this study. 30 healthy controls who are matched by IQ, race, ethnicity and age will also participate in this study. All participants are males.

Healthy subjects will only receive placebo spray. Healthy subjects will be told that they might receive placebo or oxytocin spray (one of the 3 doses). Healthy subjects will participate in one visit during which they complete questionnaires, behavioral tasks, clinical interview and training on the different tasks that they will be doing inside the MRI scanner. They will get a physical, vital signs, blood draws, placebo spray, MRI scan (including all the tasks that are described above) and behavioral tasks after the MRI scan.

ASD subjects will participate in a pre-clinical visit and will perform all the tasks and procedures that are described above. They will also participate in 4 clinical visits that will include treatment intake (syntocinon spray 8IU, 24IU, 48IU and placebo), blood draws, vital signs, MRI scan, behavioral tasks and questionnaires (see below the procedure for more details). It is a placebo-controlled randomized clinical trial, double-blind and within subject design.

Subjects will have normal or corrected-to-normal (with contact lenses) visual acuity of 20/40. MRI-compatible glasses are available for those who wear glasses rather than contact lenses. A medical history will be obtained and reviewed by the study physician or study nurse practitioner, including information about prescription and non-prescription medications.

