Given that this project is the continuity of the previous IRB protocol 64623, we will contact healthy subjects and patients with autism that were already recruited in this previous protocol. We are planning to contact those who gave us approval to be contacted (in the consent form). We will go through the screening process (see above for more details) over the phone with the patient and family member if necessary and make sure he is interested and he is eligible for the study. The study coordinator will then schedule them for the first pre-clinical visit.

If a subject withdraws from the study, we will prepare a note to file (and put it in the regulatory binder) and report to the IRB during the continuing review.

We expect to recruit at least 30 patients with autism and 20 healthy controls. We expect a drop off of patients with ASD given that they need to come for 5 visits.

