**For aim 5:**

*The primary outcome measure* consists of investigating the differences between treatment conditions in oxytocin plasma concentration in ASD. Samples of post-administration of IN-OT will be analyzed. We will conduct ANOVA repeated measures on the different OXT concentration in 4 treatment conditions.

*The secondary outcome measure* consists of studying the differences between baseline oxytocin concentration between healthy subjects and ASD. T-tests will be conducted to determine the difference between two groups.

In this protocol, we have thought of several exploratory or secondary aims that include to compare brain function and functional connectivity between healthy controls and patients with ASD in response to resting state, in response to social cues and in response to interactive social games. We will also investigate the differences in behavioral and physiological responses between ASD and healthy subjects. We will also investigate differences between these two groups (during placebo administration) in baseline plasma OXT concentration, metabolome and exposome and cytokines levels.

In our exploratory analysis, we suggested to study the different factors that could explain heterogeneity in ASD such as clinical dissociation (different kinds of social deficits), behavioral and genetic and epigenetic contribution. We will conduct separate correlation analysis for each of these aims with the severity of ASD and brain function differences with controls. It is also possible to conduct factor analysis to study which behavioral variable for instance best predict ASD severity in clinical and brain function. The same applies for the best predictors of target engagement. We believe that not all patients with ASD will benefit from IN-OT. Hence, we will study the genetic factors, epigenetic factors, clinical classifications and behavioral patterns in determining TEE-OXT or OXT-effects.

It is possible that we publish separately target engagement results (comparison between doses of OXT) and oxytocin effects (24 and 48 as compared to placebo) on the same tasks that are conducted inside the MRI scanner.

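### The plan credits 50 ASD versus 30 controls with reliable detection of a between-group Cohen's d of 0.2; the power is about 14%, against an implied 95%

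*Combined protocol and SAP*

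**What the plan says.** The power paragraph of the Statistical analysis section makes three kinds of claim. It justifies 50 ASD participants for a four-treatment within-person comparison and at least 30 healthy subjects for a within-person contrast of conditions, each time explaining reliable detection as 95% power. It then turns to healthy subjects versus ASD under placebo only and states that "the above numbers are sufficient to reliably detect small effect sizes between groups", with d=0.2 on one measure. That last sentence gives no power, alpha, sidedness or test.

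Participant selection confirms 50 ASD and adds that "30 healthy controls who are matched by IQ, race, ethnicity and age will also participate in this study". Elsewhere the expected numbers are lower. Randomization and blinding says "We believe that we will be able to test 30 patients with ASD", and the inclusion/exclusion section says "We expect to recruit at least 30 patients with autism and 20 healthy controls".

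One between-group comparison is a named secondary outcome: baseline plasma oxytocin, for which the Objectives (Aim 4) say "We expect significant difference and reduced levels of OXT at baseline in ASD". The analysis text, where this aim is numbered 5, says "T-tests will be conducted to determine the difference between two groups". The same part lists "exploratory or secondary aims that include to compare brain function and functional connectivity between healthy controls and patients with ASD", and extends the group comparison to behaviour, physiology, metabolome, exposome and cytokines.

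**The concern.** A standardised difference of 0.2 between two independent groups is small, and detecting it with high power normally takes several hundred people per group. A total of 80 is far from that, so the sentence looked wrong on its face.

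At stake is the reading of the ASD-control results. Someone who trusts the sentence would take a non-significant group difference, for example on baseline oxytocin, as evidence against even a small effect. If the true power is low, such a result says little about small or medium differences.

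**Working it through.** **Inputs.** Group sizes 50 and 30 (Statistical analysis; Participant selection); 30 ASD (Randomization and blinding); 30 and 20 (inclusion/exclusion section). Effect d=0.2, so SD=1. Test: two-sample t-test, as named for baseline oxytocin. Alpha is not stated; two-sided 0.05 is assumed and alternatives are tried.

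**Formula.** Noncentral t with df = n1 + n2 − 2 and noncentrality d × √(n1·n2/(n1 + n2)), both tails counted.

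**The plan's figure.** For 50 and 30: √(1500/80) = 4.330, noncentrality 0.2 × 4.330 = 0.866, df 78, critical t 1.991. Power is 13.7%, so the implied 95% is not reproduced. One-sided 0.05 gives 21.6%; two-sided 0.10 gives 22.2%.

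**All group sizes, two-sided 0.05.**

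| ASD / controls | Power, d=0.2 | Power, d=0.5 | Power, d=0.8 | Detectable d, 95% power | Detectable d, 80% power |
|---|---|---|---|---|---|
| 50 / 30 | 13.7% | 57% | 93% | 0.84 | 0.66 |
| 30 / 30 | 11.9% | 48% | 86% | 0.95 | 0.74 |
| 30 / 20 | 10.4% | 40% | 78% | 1.06 | 0.83 |

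**Size needed.** With equal groups, d=0.2 reaches 95% power at 651 per group.

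**Precision.** The 95% confidence interval half-width is t(0.975, df) × √(1/n1 + 1/n2). This is 1.991 × 0.2309 = 0.46 SD at 50 versus 30 and 2.011 × 0.2887 = 0.58 SD at 30 versus 20. Both are more than twice the effect said to be detectable.

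**Readings that might rescue the sentence.**

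- *Matched pairs.* With 30 pairs the paired effect is 0.2/√(2(1 − r)). A within-pair correlation r of 0.5 gives 19% power and 0.9 gives 66%; 95% needs about 0.96.
- *Contrast scores*, such as emotional minus neutral faces, with d on the single-condition SD, 50 versus 30. A between-condition correlation of 0.5 gives 14% and 0.9 gives 48%; 95% needs about 0.97.
- *0.2 entered as Cohen's f.* For a group-by-condition interaction with 80 people in equal groups, 2 conditions and correlation 0.5, lambda = 0.2² × 80 × 2/(1 − 0.5) = 12.8 and power is 94%. With 40 per group, n1·n2/(n1 + n2) = 20, so this equals d = √(12.8/20) = 0.80 on the contrast score. A plain two-group comparison with f=0.2 reaches only 42%.

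**The case against.** The sentence states neither a power nor an alpha, so 95% is inferred, and a t-test is named only for baseline oxytocin, not for the imaging, behavioural or physiological comparisons. Both points are fair. Neither rescues the claim: it also fails against 80% power, and the alternative alphas and analyses above leave it far short unless correlations are extreme.

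The Cohen's f reading may explain how the sentence arose, since it comes close to 95%. That is an inference. The text says Cohen's d, small and between groups, and under the f reading the effect is a large one.

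The weight of the error is limited. The comparisons are secondary or exploratory, the 50 and the 30 are justified by within-person comparisons, and nowhere does the plan say that a null group result will be read as absence of a difference. This stands, and it keeps the point below anything that threatens the primary analysis.

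Finally, 50 versus 30 may no longer be attainable. The section on screening healthy subjects says patient testing is already complete, without giving the final number. This also stands and bears on the fix. If the ASD group is smaller than 50, power falls further.

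**Conclusion.** The concern holds. With 50 ASD and 30 controls, power for d=0.2 is about 14%, not the implied 95%; at the lower expected numbers it is 10% to 12%. This rests on a two-sample t-test at two-sided alpha 0.05, both assumed for most of the comparisons, but the conclusion does not depend on that choice.

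The trial can usually find a large group difference (d=0.8: 93% power at 50 versus 30, 78% at 30 versus 20). It would miss a medium one of d=0.5 in 43% of cases at 50 versus 30 and 60% at 30 versus 20.

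This should be fixed. The sentence does not bear on the within-ASD primary outcomes. The other power figures in the same paragraph are a separate question, and nothing here clears them.

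**What to change.** Replace the sentence with the detectable effect at the actual number of ASD participants tested and the number of controls obtained or still expected, naming the test, alpha and sidedness. For a two-sample t-test at two-sided alpha 0.05, the entry would read d=0.84 at 95% power or 0.66 at 80% if the groups are 50 and 30, and d=1.06 or 0.83 if they are 30 and 20.

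Add a reporting line: ASD-control differences are given with 95% confidence intervals, and a non-significant result is not taken as absence of a difference.

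The cost is one sentence and one reporting line. Enrolment and procedures stay as they are; the only downside is a less favourable stated figure.
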